10.3 Hypotheses/Estimation

Objectives and hypotheses of the study are stated in Section 4.

10.4 Analysis Endpoints

The efficacy, immunogenicity, and safety endpoints that will be evaluated are listed below.

10.4.1 Efficacy Endpoints

The efficacy endpoint that will be used to evaluate VE and test the primary and secondary efficacy hypotheses is the number of participants with primary CMVi, described in Section 4 and Section 5.4.1.

CMVi is defined as detection of CMV DNA by PCR in urine or saliva samples.

As stated in Section 4, in the evaluation of the primary and secondary efficacy hypotheses, cases of CMVi will be counted starting after the last dose of the assigned vaccination regimen. As stated in Section 10.5.1, the primary and secondary efficacy hypothesis will be evaluated on the PPE population, where eligibility includes being PCR negative post Day 1 through Month 7. Thus, CMVi cases that will be included in the PPE testing of the primary and secondary efficacy hypothesis are those that occurred after Month 7.

10.4.2 Immunogenicity Endpoints

All immunogenicity endpoints in this study are exploratory endpoints and are listed below. These will be further described and defined in a sSAP that will be written for this study.

- Seroconversion based on the NAb and IgG ELISA assays, defined as transition from CMV seronegative at Day 1 to CMV seropositive at Month 7.
- Seropositivity based on the NAb and IgG ELISA assays at Day 1, Months, 7, 12, 24, and 36.
- GMTs based on the NAb and the IgG ELISA assays at Day 1, Months 7, 12, 24, and 36.
- GMc of SFC/10⁶ PBMCs based on the ELISPOT assay Day 1, Months 6, 7, 12, and 24.

10.4.3 Safety Endpoints

As specified in Section 4, Section 5.4.1.3, and Section 10.6.3, the endpoints that will be used to assess the safety and tolerability of 2-dose and 3-dose regimens of V160 include the following:

- Number of participants experiencing solicited injection site AEs within Days 1 through 5 after each vaccination visit; solicited systemic AEs (including tiredness, muscle pain, headache, and joint pain); and vaccine-related systemic AEs, SAEs, and elevated temperatures within Days 1 through 14 after each vaccination visit
- Incidence of any SAE at any time during the study

- Incidence of vaccine-type viral shedding
- Outcomes of pregnancies.

10.5 Analysis Populations

10.5.1 Efficacy Analysis Populations

Per Protocol Efficacy (PPE)

The PPE population will serve as the primary population for the evaluation of VE and for testing the primary and secondary efficacy hypotheses. To be eligible for inclusion in the PPE population, study participants must satisfy the following criteria:

- CMV seronegative at Day 1 and CMV negative by PCR for non-vaccine strain virus from post Day 1 through Month 7
- Have received all 3 injections/vaccinations within the vaccination visit window specified in the SoA (Section 2)
- At any time from Day 1 through Month 7, did not have events, deviations from protocol, or engaged in activities that are deemed by the study Clinical Director to potentially interfere with the evaluation of efficacy or immune response to injections of V160.

Participants whose CMV status by PCR post Day 1 through Month 7 is not evaluable will be ineligible for inclusion in the PPE population. The categories of events, deviations from protocol, or activities that are deemed by the study Clinical Director to potentially interfere with the evaluation of efficacy or immune response to injections of V160 will be identified and documented in a memo to study file prior to the time of the IA for efficacy assessment.

Full Analysis Set (FAS)

The FAS will serve as a supportive analysis population for the evaluation of VE. The FAS population consists of all randomized participants who received at least 1 dose of the correct clinical material corresponding to the treatment regimen the participants were randomized into.

10.5.2 Immunogenicity Analysis Populations

The immunogenicity analysis populations that will be used in exploratory analyses of immunogenicity will be described in the sSAP that will be written for this study.

10.5.3 Safety Analysis Population

All Participants as Treated (APaT)

The APaT population will serve as the primary population for evaluation of safety. The APaT population includes all randomized participants who received at least 1 injection of V160 or placebo, have safety follow-up data, and assigns participants to the treatment arm corresponding to the actual clinical material received. For participants who received injections of V160 or placebo corresponding to a sequence that does not correspond to any of

the protocol-defined treatment arms (ie, cross-treated participants), a safety profile listing will be created separate from the safety reports that will be provided for the protocol-defined treatment arms.

10.6 Statistical Methods

Statistical testing and inference relating to efficacy are described in Section 10.6.1. Statistical methods relating to safety analyses are described in Section 10.6.3. Efficacy results that will be deemed to be statistically significant after consideration of the Type 1 error control strategy are described in Section 10.8. Nominal p-values may be computed for other efficacy analyses, but should be interpreted with caution due to potential issues of multiplicity, sample size, etc. Unless otherwise stated, all statistical tests will be conducted at the $\alpha=0.025$ (1-sided) level.

10.6.1 Statistical Methods for Efficacy Analyses

To address the primary and secondary efficacy hypotheses, one-sided tests of the null hypothesis that the vaccine efficacy is 0% versus the alternative that vaccine efficacy is >0% will be conducted separately for each of the primary and secondary hypotheses. Each of the primary and secondary efficacy hypotheses will be tested at one-sided $\alpha=0.025$ level (ie, 2.5% Type 1 error). Vaccine efficacy is defined as:

$$VE = 100\% * \{1 - (R_v/R_p)\}$$

where R_v and R_p are the incidence rates CMVi in the V160 dose regimen (3-dose for the primary efficacy hypothesis testing; 2-dose for the secondary efficacy hypothesis testing) and placebo groups, respectively. The incidence rate R_v is defined as $R_v = C_v/T_v$, where C_v = the count of CMVi cases in the vaccine group and T_v = total person-years of follow-up for efficacy in the vaccine group. The incidence rate R_p is defined similarly. The null hypothesis that vaccine is not efficacious (ie, $VE=0\%$) will be tested by constructing a $100*(1-\alpha)\%$ confidence interval (CI) for VE, denoted as (VE_L, VE_U) , based on study data at a particular analysis time point (eg, at IA or at final analysis). The statistical criterion for success with respect to the primary efficacy hypothesis (and likewise for the secondary efficacy hypothesis) will be met if $VE_L > 0\%$.

The $100*(1-\alpha)\%$ CI for VE, (VE_L, VE_U) , is constructed as follows. Under the assumption that R_v and R_p are the means of independent Poisson processes, and given that there is a total of $n = C_v + C_p$ efficacy endpoint cases observed in the combined V160 dose regimen and placebo groups, then the number of primary efficacy cases C_v in the V160 dose regimen group is distributed as Binomial(n, π), where the binomial probability π is defined as $\pi = T_v R_v / (T_v R_v + T_p R_p)$. The probability π is a person-years-adjusted estimate of the probability that a particular study participant who became a case of CMVi belongs to the V160 dose regimen group. The lower bound of the $100*(1-\alpha)\%$ exact CI for the probability π is obtained by searching for the proportion π_L such that the probability of observing C_v or more efficacy endpoint cases out of n total efficacy cases is $\leq \alpha/2$. Similarly, the upper bound of the $100*(1-\alpha)\%$ exact CI for the probability π is obtained by searching for the proportion π_U such that the probability of observing C_v or fewer efficacy endpoint cases out of n total

efficacy cases is $\leq \alpha/2$ [Chan, I. S. F. and Bohidar, N. R. 1998]. VE_L and VE_E are then calculated from π_L and π_U as follows:

$$VE_L = 100\% * \{1((U, (1+0))/(1-\pi_U));$$
$$VE_U = 100\% * \{1((L, (1+0))/(1-\pi_L));$$

where $\theta = T_p/T_v$ is the ratio of the total person-years of follow-up for efficacy in the placebo group over the V160 dose regimen group.

There is only one final analysis of the secondary efficacy endpoint. However, the testing of the secondary efficacy hypothesis may occur at the time of the IA or the final analysis of the primary efficacy hypothesis. The secondary efficacy hypothesis will only be tested if the primary efficacy hypothesis is successfully demonstrated. In addition, the secondary efficacy hypothesis will be tested contingent on accumulation of ≥ 15 total CMVi cases in the V160 2-dose and placebo regimens (see [Figure 2](#) in Section 10.7, and Section 10.9.1.2). Thus, the possible timing for testing the secondary hypothesis is as follows.

- If the primary hypothesis test is successful at the IA *and* there are ≥ 15 total CMVi cases in the V160 2-dose and placebo regimens at the time of IA, then the secondary efficacy hypothesis will be tested immediately after the testing of the primary efficacy hypothesis at the time of the IA.
- If the primary hypothesis test is successful at the IA and there are < 15 total CMVi cases in the V160 2-dose and placebo regimens at the time of IA, the secondary efficacy hypothesis will not be tested at the IA. In this case, follow-up will continue until at least 15 total CMVi cases in the V160 2-dose and placebo regimens groups are accrued. Upon accrual of ≥ 15 total CMVi cases in the V160 2-dose and placebo regimens, the secondary efficacy hypothesis will be tested.
- If the primary hypothesis test is not successful at the IA, the secondary efficacy hypothesis will not be tested at the time of the IA.

10.6.2 Statistical Methods for Immunogenicity Analyses

Statistical methods for analysis of exploratory immunogenicity endpoints will be provided in the sSAP that will be written for this study.

10.6.3 Statistical Methods for Safety Analyses

Safety and tolerability will be assessed by clinical review of all relevant parameters including AEs and outcomes of pregnancies.

The analysis of safety results will follow a tiered approach ([Table 5](#)). The tiers differ with respect to the analyses that will be performed. Safety parameters or adverse events of special interest that are identified *a priori* constitute “Tier 1” safety endpoints that will be subject to inferential testing for statistical significance with p-values and 95% confidence intervals provided for between-group comparisons. Other safety parameters will be considered Tier 2 or Tier 3. Tier 2 parameters will be assessed via point estimates with 95% confidence intervals provided for V160 dose regimen versus placebo comparisons; only point estimates by treatment group are provided for Tier 3 safety parameters. Safety results will be summarized for each vaccination dose and across all three vaccination doses.

There were no SAEs nor vaccine-type viral shedding (which is an event of interest for V160) observed in the V160 Phase I study. While vaccine-type viral shedding is an event of interest that can occur only in V160-vaccinated subjects, barring false-positive tests in placebo recipients, the 0% incidence of vaccine-type viral shedding observed in the Phase I study provides no informed, data-driven, non-zero incidence level around which a safety hypothesis can be formulated and tested. Therefore, there is no *a priori* identified AE or ECI for which a test of hypothesis will be conducted. Thus, no Tier 1 event is identified in this study. Categories of events considered as Tier 2 and Tier 3 in this study are shown in [Table 5](#). In addition, AEs observed in at least 7 participants (representing 1% of N=700 participants per group) in any vaccination group will be categorized as a Tier 2 event. Incidences of the categories of events identified in [Table 5](#) will be reported as percentages, generally calculated as $100\% \times (\text{number of participants who experienced the event} / \text{total number of participants with safety follow-up})$, except for outcomes of pregnancies, SAEs throughout the study duration, and vaccine-type viral shedding. The 95% CIs will be provided for vaccine versus placebo percentage point differences (percent in V160 dose regimen group minus percent in placebo) will be calculated using the Miettinen and Nurminen method [Miettinen, O. and Nurminen, M. 1985], an unconditional, asymptotic method. No stratification factor will be used in the calculation of 95% CI.

Percentages of outcomes of pregnancies will be generally calculated as $100\% \times (\text{total number of specific pregnancy outcome being reported} / \text{total number of all relevant pregnancy outcomes})$. For example, the percent associated with the pregnancy outcome of *live births* will be calculated as $100\% \times (\text{total number of live births} / \text{total number of fetuses/infants with known outcomes})$. The numerator and denominator account for pregnancies with multiple fetuses (ie, twins, triplets, etc.) and do not treat such occurrences as a single pregnancy outcome or event. Further details will be provided in the sSAP that will be written for this study.

Vaccine-type viral shedding will be assessed in V160-vaccinated participants. In addition to the analysis strategy shown in [Table 5](#), point and corresponding 95% CI estimates of incidence of vaccine-type viral shedding (number of participants observed with vaccine-type viral shedding/total person-years of follow-up) will be calculated separately for the V160 3-dose, V160 2-dose, and placebo arms. No treatment group comparisons (V160 vs. placebo or V160 3-dose vs. 2-dose arms) of the percent of participants detected with vaccine-type viral shedding will be conducted.

Summaries of SAEs (throughout the study duration) by system organ class will be provided as incidence rates (number of participants [or infants] observed with a specific SAE/total person-years of follow-up) rather than percentages.

Table 5 Analysis Strategy for Safety Parameters

| Safety Tier | Safety Endpoint | p-value | 95% CI for Comparison of V160 to Placebo | Descriptive Statistics |
|-------------|-------------------------------------------------------------------------------|---------|------------------------------------------|------------------------|
| Tier 2 | Solicited injection site AEs ^a | | X | X |
| | Solicited systemic AEs | | X | X |
| | Vaccine-related systemic AEs | | X | X |
| | Any serious AEs (in study participants or infants born to study participants) | | X | X ^b |
| | Vaccine-related serious AEs within Days 1 through 14 after vaccination | | X | X |
| | Discontinuations due to AEs | | X | X |
| | Elevated temperature ^c | | X | X |
| | AEs by SOC observed in ≥7 participants in at least one vaccination group | | X | X |
| Tier 3 | AEs by SOC | | | X |
| | Outcomes of pregnancies | | | X |
| | Vaccine-type viral shedding | | | X [‡] |

^a All injection site AEs are considered vaccine-related.
^b Incidence rates (cases/total person-years follow-up) will be provided instead of percentages.
^c Defined as ≥38.0°C [≥100.4°] oral or equivalent
 AE = Adverse event; CI = Confidence interval; SOC = System organ class; X = indicated summary statistic will be provided.

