6.1 Inclusion Criteria

Participants are eligible to be included in the study only if all of the following criteria apply:

1. Healthy, based on medical history and physical examination
2. Female, 16 to 35 years of age
3. Serologically confirmed as CMV seronegative (based on CMV IgG) prior to receiving the first dose of V160/placebo
4. Have direct exposure to young children (≤ 5 years of age) at home or occupationally
5. Childbearing potential (see definition of women of childbearing potential [WOCBP] in Appendix 3)
6. Agrees to avoid becoming pregnant during the 6-month treatment phase and for 4 weeks after the last dose of V160/placebo (from Day 1 through Month 7) by either practicing abstinence from heterosexual activity OR by using allowable methods of birth control during heterosexual activity. Allowable methods of birth control are provided in the Appendix 3.

Informed Consent/Assent

7. Voluntarily agrees to participate (or legally acceptable representative, for minors, if applicable); and provide written informed consent/assent for the trial. The participant may also provide consent/assent for Future Biomedical Research. However, the participant may participate in the main trial without participating in Future Biomedical Research.

Protocol Adherence

8. Be able to complete all scheduled visits and to comply with the study procedures
9. Agrees to provide study personnel with a primary telephone number as well as an alternate form of contact, if available, for follow-up purposes

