 - a. saliva, urine, or other body fluid samples (including the neonatal dried blood spot) obtained within 21 days of birth from an infant born to a study participant;

OR

 - b. amniocentesis fluid obtained from a study participant, or samples from still-birth or products of conception obtained from a study participant.

9.2.1.2.2 cCMVi Case Detection

After a pregnancy is reported to the site, the participant will be asked to come to the site for a study visit (referred to as cCMVi Visit 1).

At this visit, the site staff will explain that the participant's pregnancy will be monitored via monthly contacts from the site until the outcome of the pregnancy is established and recorded. Instructions on when to call the site for any changes in pregnancy status will be provided and an explanation and informed consent/assent regarding follow-up of infant/live birth will also be provided.

For the pregnancy follow-up, medical records of the pregnant study participant will be collected and reviewed by the site personnel to:

- confirm date of conception and expected delivery date
- obtain information on the outcome of the pregnancy
- obtain information that could indicate a suspicion/diagnosis of congenital CMV infection and whether the participant had any related interventions
 - Any anti-CMV treatments received by participants during pregnancy or by infants will be collected for the duration of the trial.
- obtain information that could indicate suspected congenital infection in the infant

All relevant medical records should be placed in the participant's trial file. Infant outcomes will be recorded in the eCRF for all pregnant participants within 24 hours of the delivery or as soon as possible. All pregnancies will be followed to outcome. Refer to Section 9.3.6 for additional requirements for pregnancy follow-up and reporting.

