9.3.3 Follow-up of AE, SAE and Other Reportable Safety Event Information

After the initial AE/SAE report, the investigator is required to proactively follow each participant at subsequent visits/contacts. All AE, SAE and other reportable safety events including pregnancy and exposure during breastfeeding, Cancer and Overdose will be followed until resolution, stabilization, until the event is otherwise explained, or the participant is lost to follow-up (as defined in Section 8.3). In addition, the investigator will make every attempt to follow all non-serious AEs that occur in randomized participants for outcome. Further information on follow-up procedures is given in Appendix 4. Although participants are to agree not to become pregnant during the vaccination period through Month 7, if a pregnancy is reported before the last planned V160/placebo dose, the participant will be discontinued from further planned vaccination regimen per exclusion criterion but will not be discontinued from the study. Participants who inadvertently become pregnant before receiving all 3 doses of study vaccine or placebo, and any participant who becomes pregnant after the treatment phase will remain in the trial for follow-up of pregnancy and outcome.

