There were no SAEs nor vaccine-type viral shedding (which is an event of interest for V160) observed in the V160 Phase I study. While vaccine-type viral shedding is an event of interest that can occur only in V160-vaccinated subjects, barring false-positive tests in placebo recipients, the 0% incidence of vaccine-type viral shedding observed in the Phase I study provides no informed, data-driven, non-zero incidence level around which a safety hypothesis can be formulated and tested. Therefore, there is no *a priori* identified AE or ECI for which a test of hypothesis will be conducted. Thus, no Tier 1 event is identified in this study. Categories of events considered as Tier 2 and Tier 3 in this study are shown in Table 1. In addition, AEs observed in at least 7 participants (representing 1% of N=700 participants per group) in any vaccination group will be categorized as a Tier 2 event. Incidences of the categories of events identified in Table 1 will be reported as percentages, generally calculated as $100\% \times (\text{number of participants who experienced the event} / \text{total number of participants with safety follow-up})$, except for outcomes of pregnancies, SAEs throughout the study duration, and vaccine-type viral shedding. The 95% CIs will be provided for vaccine versus placebo percentage point differences (percent in V160 dose regimen group minus percent in placebo) will be calculated using the Miettinen and Nurminen method [2], an unconditional, asymptotic method. No stratification factor will be used in the calculation of 95% CI.

Percentages of outcomes of pregnancies will be generally calculated as $100\% \times (\text{total number of specific pregnancy outcome being reported} / \text{total number of all relevant pregnancy outcomes})$. For example, the percent associated with the pregnancy outcome of *live births* will be calculated as $100\% \times (\text{total number of live births} / \text{total number of fetuses/infants with known outcomes})$. The numerator and denominator account for pregnancies with multiple fetuses (ie, twins, triplets, etc.) and do not treat such occurrences as a single pregnancy outcome or event. Further details will be provided in the sSAP that will be written for this study.

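### Pregnancy outcomes are summarised over one denominator per arm with no split by conception timing relative to dosing, and the sSAP defers the detail to itself

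*Combined protocol and SAP*

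**What the plan says.** Outcomes of pregnancies are a listed safety endpoint (protocol 10.4.3, sSAP 3.4.3). They are Tier 3 in Table 5 of the protocol and Table 1 of the sSAP, and for that tier "only point estimates by treatment group are provided for Tier 3 safety parameters".

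The calculation is in protocol 10.6.3: "Percentages of outcomes of pregnancies will be generally calculated as" the number with a given outcome over the total of relevant outcomes. The worked example puts all live births over all fetuses or infants whose outcome is known. The counting unit is settled ("The numerator and denominator account for pregnancies with multiple fetuses"), but nothing is said about conception date. The paragraph ends by handing the detail to the sSAP. Section 3.6.3 of the sSAP repeats the paragraph and ends with the same promise: "Further details will be provided in the sSAP that will be written for this study". The sSAP's summary of changes (2.1 and 2.2) lists nothing on pregnancy.

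Elsewhere the protocol does distinguish timing:

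- Inclusion criterion 6 (section 6.1): the participant "Agrees to avoid becoming pregnant during the 6-month treatment phase and for 4 weeks after the last dose", glossed there as Day 1 through Month 7.
- Appendix 3, Table 9 notes: pregnancy is allowed once the treatment phase is over.
- Sections 9.3.3 and 9.3.6: "Participants who inadvertently become pregnant before receiving all 3 doses of study vaccine or placebo" stay in follow-up, as do those who conceive later.
- Section 9.2.1.2.2: medical records are reviewed to "confirm date of conception and expected delivery date".

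**The concern.** The avoidance window exists because pregnancies begun close to dosing are the ones for which vaccine exposure is the obvious question. The specified summary puts them in the same percentage as pregnancies begun months or years after the last dose. If contraception works as required, the in-window group is a small minority, so even a large excess of losses or anomalies among them would hardly change the reported figure. A placebo-like percentage could then be read as reassurance about exposure in pregnancy when very few exposed pregnancies lie behind it.

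The protocol already uses a window for the parallel question. Lactation exposure is reportable only from Day 1 through Month 7 (Table 4), and breastfeeding that starts after the treatment phase need not be reported (9.3.6). The analysis of pregnancy outcomes has no equivalent.

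**Working it through.** **The plan's own figures.** No precision or count is stated for pregnancy outcomes. The nearest figures, in protocol 10.9.2, use 700 participants per arm, and they reproduce:

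- At least one event at incidence 1/150: 1 − (1 − 1/150)^700 = 99.07% (stated as above 99%).
- At least one event at incidence 1/300: 1 − (1 − 1/300)^700 = 90.34% (stated as above 90%).
- Upper 97.5% limit for 0 of 700: 1 − 0.025^(1/700) = 0.526% (stated as 0.5%).

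These describe all vaccinees. They do not describe what the trial can say about pregnancies.

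**Inputs from the documents.** 700 per arm (10.9.1.1). Avoidance window of 7 months (6.1). Contraceptive failure below 1% per year with consistent and correct use (Appendix 3, Table 9). Enrolment over 18 months in a trial of about 3 years (Synopsis).

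**Assumptions, not in the documents.** Uniform enrolment and no loss to follow-up; later pregnancy rates of 2%, 5%, 10% or 15% per year; a background loss rate of 15%; loss doubled to 30% for in-window pregnancies on vaccine.

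**Step 1, in-window conceptions per arm.** 700 × 7/12 × 1% = 4.1.

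**Step 2, follow-up after Month 7.** The first enrolled have 36 − 7 = 29 months and the last have 36 − 18 − 7 = 11. The mean is 36 − 9 − 7 = 20 months, or 20/12 years.

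**Step 3, later pregnancies per arm.** 700 × 20/12 × rate.

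**Step 4, combined loss percentage.** With s = in-window / (in-window + later), the combined figure is s × 30% + (1 − s) × 15% = 15% + 15 points × s.

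| Later rate per year | Later pregnancies | In-window share s | Combined loss | Shift |
|---|---|---|---|---|
| 2% | 23 | 14.9% | 17.2% | 2.2 points |
| 5% | 58 | 6.5% | 16.0% | 1.0 point |
| 10% | 117 | 3.4% | 15.5% | 0.5 point |
| 15% | 175 | 2.3% | 15.3% | 0.3 point |

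**Step 5, sensitivity to contraceptive failure.** At five times the ceiling there are about 20 in-window conceptions. With 5% per year later, the share is 26% and the combined figure 18.9%. The largest share among the scenarios run is 49% (five times the ceiling, 2% per year later, 7% yearly loss to follow-up), which gives 22.4%. Even there about half of the 15-point excess is lost.

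**Step 6, what a separate group could show.** With 4 in-window pregnancies per arm, the expected losses are 4 × 30% = 1.2 against 4 × 15% = 0.6. If no event is seen, the upper 97.5% limit is 1 − 0.025^(1/n): 60% for n = 4, 37% for n = 8 and 17% for n = 20.

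**Other summaries.** The by-dose sentence ("Safety results will be summarized for each vaccination dose and across all three vaccination doses") does not mention conception date, so it does not separate a conception one week after the third injection from one two years later. The SAE summaries in Table 5 and the rates by system organ class cover the whole study and are not split by conception timing.

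**The case against.** The strongest reply is that harm in exposed pregnancies has other routes to notice. Section 9.3.6 requires spontaneous abortion, fetal death, stillbirth and similar outcomes to be reported as serious events. Appendix 4 makes a congenital anomaly in offspring an SAE and asks for a causality assessment that considers exposure and time course. SAEs in participants or infants are Tier 2 with a 95% CI against placebo, and the eDMC reviews cumulative safety data at the interim. All of this stands. A reader might infer that the pooled percentage is the plan's only summary of harm in pregnancy; the documents do not support that. These routes allow case-by-case review, but none of their summaries separates in-window from later conceptions.

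Four other stronger readings are tempting and should also be set aside:

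- *That the plan chose to pool.* It gives one undifferentiated denominator and neither states nor excludes a split. *Relevant* is undefined.
- *That later pregnancies are unexposed and in-window ones the only exposed ones.* No section defines an exposure window for pregnancy. Appendix 5 says the PCR assay will help assess whether V160 can establish latency, although this is not expected. Timing relative to dosing is the most that can be said.
- *That later pregnancies accrue over two years or more for everyone.* Mean planned follow-up after Month 7 is about 20 months. Only those enrolled in the first 36 − 7 − 24 = 5 of 18 months (28%) would reach two years.
- *That a separate table would show a clear 30% against 15%.* Those rates are assumed, and with about 4 pregnancies per arm the contrast is roughly one loss against one or none. A percentage on 4 pregnancies can mislead as readily as a combined one.

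It is also fair to say that this is a descriptive endpoint with no bearing on the efficacy hypotheses or Type 1 error.

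**Conclusion.** The point holds as a gap in the safety analysis, and closing it is worthwhile and cheap. As specified, pregnancies conceived in the protocol's avoidance window are combined with later permitted ones in each arm, and the promised detail is missing because the sSAP refers to itself. This rests on the text alone.

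The size is conditional. With about 4 in-window conceptions per arm (the 1% per year ceiling applied to all 700 women) and later pregnancy rates of 2% to 15% per year, a doubling of a 15% loss rate appears as a shift of 2.2 down to 0.3 points. The later pregnancy rates, the background loss rate and the doubling are assumptions. Use of contraception that falls short of consistent and correct would enlarge the in-window group and reduce the dilution, but that group stayed a minority in every scenario run. The documents do not support a claim that a split would give a readable statistical signal. Its value is to show how few in-window pregnancies there are and what happened in each.

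**What to change.** In sSAP 3.6.3, before the study team is unblinded:

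1. Define *relevant* in the denominator and replace the sentence that defers to the sSAP.
2. Using the conception date already confirmed from medical records, tabulate pregnancy outcomes and infant SAEs by arm for (a) conception from before Dose 1 through 4 weeks after the last dose received, and (b) later conception. Starting (a) before Dose 1 captures a pregnancy undetected at vaccination.
3. List each pregnancy in (a) individually, with the number of V160 doses received and the interval from the last dose.
4. Keep the pooled table alongside.

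State that (a) is descriptive, with counts shown beside any percentage and no formal comparison.

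The cost is a few lines of wording, one table and one listing. No new data are needed, and the efficacy analysis is untouched. The drawback is small counts in (a), which is why the listing matters more than the percentages. If the window is not fixed in advance, it would have to be chosen with the results in view.
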